6.4 Clinical Assessments and Procedures

Calculations or measurements of specific parameters are required as indicated in the Schedule of Assessments. Instructions for determining these parameters are provided in the following sections.

6.4.1 Physical Examination

A physical examination (excluding breast, rectal/vaginal examination) will be performed by a physician at baseline. Physical examination will include a standard neurological examination.

6.4.2 Vital Signs

Vital signs will include temperature (measured orally), blood pressure (mm Hg), and heart rate (beats/minute). Vital signs will be measured in the seated position after at least 5 minutes of rest in this position.

6.4.3 Compliance

Compliance will be assessed by counting the returned tablets at each visit. Compliance is calculated by determining the number of tablets taken divided by the number of tablets expected to have been taken.

$$\frac{\text{number of tablets taken}}{\text{number of tablets expected to be taken}} \times 100\%$$

6.5 Laboratory Analysis

Blood samples will be drawn at each study visit as indicated in the Schedule of Assessments.

Protection of subject confidentiality will extend to all data generated from the assaying of these samples. The samples will be alphanumerically coded and the persons performing the analysis will not be aware of the subject's identity.

Whole blood will be collected into EDTA tubes for CBC (includes WBC differential) and T lymphocyte counts (CD4+, CD8+). Serum will be generated from blood collected into SST tubes for electrolytes (Na, K, Cl), glucose, creatinine, AST, ALT, GGT, bilirubin, TNF α , and IL-8.

The urine pregnancy test will be performed at the clinic site.

7. Safety Instructions and Guidance

7.1 Adverse Events and Laboratory Abnormalities

7.1.1 Adverse Events

An adverse event (AE) is any untoward medical occurrence in a clinical investigation subject who has been administered an investigational product and which does not necessarily have a causal relationship with this treatment. An AE can be any unfavorable and unintended sign (including an abnormal laboratory finding), symptom, or disease temporally associated with the

A Pilot Study to Investigate the Effects of Humic Acid on Flu Symptoms

Protocol 10HFHL

use of a product, whether or not it is considered related to that product. Pre-existing conditions which worsen during a study are to be reported as AEs. Flu symptoms are recorded daily by the subject and may worsen during the trial. These events will be captured as daily symptom scores and are not to be recorded as separated adverse events.

During the study, subjects should record any adverse effects in their diary. At each visit the subject will be asked "Have you experienced any difficulties or problems since I saw you last"? Any (AEs) will be documented in the study record and will be classified according to the description, duration, intensity, frequency, and outcome. The investigator will assess any AEs and decide causality.

Intensity of AEs will be graded on a three-point scale (mild, moderate, severe) and reported in detail in the study record:

Mild:	Awareness of event but easily tolerated
Moderate:	Discomfort enough to cause some interference with usual activity
Severe:	Inability to carry out usual activity

The causality relationship of investigational product to the adverse event will be assessed by the investigator as either:

Most probable:	There is a reasonable relationship between the investigational product and AE. The event responds to withdrawal of investigational product (dechallenge) and recurs with rechallenge when clinically feasible.
Probable:	There is a reasonable relationship between the investigational product and AE. The event responds to dechallenge.
Possible:	There is a reasonable relationship between the investigational product and AE. Dechallenge information is lacking or unclear.
Unlikely:	There is a temporal relationship to investigational product administration but there is no reasonable causal relationship between the investigational product and the AE.
Not related:	No temporal relationship to the investigational product administration or there is a reasonable causal relationship between non-investigational product, concurrent disease or circumstance and the AE.

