4.1 Inclusion Criteria

1. Male or female age 18 years or older
2. If female, subject is not of child bearing potential. Defined as females who have had a hysterectomy or oophorectomy, bilateral tubal ligation or are post-menopausal (natural or surgically with > 1 year since last menstruation)

–OR:

A Pilot Study to Investigate the Effects of Humic Acid on Flu Symptoms

Protocol 10HFHL

Female subjects of childbearing potential must agree to use a medically approved method of birth control and have a negative urine pregnancy test result. Acceptable methods of birth control include:

- double-barrier method (condoms with spermicide or diaphragm with spermicide)
 - hormonal contraceptives including oral contraceptives, hormone birth control patch (Ortho Evra), vaginal contraceptive ring (NuvaRing), injectable contraceptives (Depo-Provera, Lunelle), or hormone implant (Norplant System)
 - intrauterine devices
 - vasectomy of partner
 - abstinence
3. Positive diagnostic testing for influenza A or B by using rapid influenza antigen test (nasopharyngeal swabs)
 4. Illness as defined by onset or presence of respiratory symptom (cough, sore throat, nasal symptoms, sneezing) and one the following symptoms beginning within 48 hours before study enrollment:
 - fever ≥ 38.0 °C (≥ 100.4 °F) taken orally or subject report of fever within 24 hours prior to screening.
 - constitutional symptom [headache, myalgia (muscle pain), sweats/chills, fatigue]
 5. Available for all the visits scheduled in the study
 6. Receipt of any vaccine against influenza (based on verbal confirmation by the subject) for current season will be allowed
 7. Agreement to comply with study procedures and test article consumption
 8. Has given voluntary, written, informed consent to participate in the study

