Appendix 2. Flu Symptoms Questionnaire

Subjects will be asked to indicate by means of interview all symptoms present at screening in order to assess eligibility. Investigator or designate will record the presence of the following symptoms:

Respiratory symptoms

1. *Cough*
2. *Sore throat*
3. *Nasal symptoms*
4. *Sneezing*

Fever

5. ≥ 38.0 °C (≥ 100.4 °F) taken orally
6. *Subject report of fever within the past 24 hours*

Constitutional symptoms

7. *Headache*
8. *Myalgia (muscle pain)*
9. *Sweats/chills*
10. *Fatigue*

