Appendix 3. Daily Symptoms Scores

Subjects will be asked to rate how severe their flu symptoms are by means of a self-administered questionnaire to be completed daily. Each response will be based on a 4-point scale:

- 0 = *absent*
1 = *mild*
2 = *moderate*
3 = *severe*

Symptoms

1. *Cough*
2. *Fever*
3. *Runny nose*
4. *Stuffy nose*
5. *Aches and pains*
6. *Headache*
7. *Chills*
8. *Sneezing*
9. *Ear aches*
10. *Fatigue*

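### Section 7.1.1 exempts worsening flu symptoms from adverse event recording with no exception for worsening the investigator suspects is due to the product

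*Protocol*

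**What the plan says.** Section 7.1.1 first gives the general rule: "Pre-existing conditions which worsen during a study are to be reported as AEs". It then notes that flu symptoms are kept in the daily record and may get worse, and directs: "These events will be captured as daily symptom scores and are not to be recorded as separated adverse events". No condition is attached.

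The next paragraph sets out how AEs are found and judged. For subjects, "During the study, subjects should record any adverse effects in their diary". An open question about problems is asked at each visit, and "The investigator will assess any AEs and decide causality".

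Section 7.1.1 does not list the flu symptoms, but other sections do:

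- Inclusion criterion 4 (Section 4.1) defines the illness by a respiratory symptom (sore throat is one of those named) plus fever or a "constitutional symptom [headache, myalgia (muscle pain), sweats/chills, fatigue".
- Appendix 2 repeats these symptoms for screening.
- Appendix 3 covers the daily scores: "Subjects will be asked to rate how severe their flu symptoms are by means of a self-administered questionnaire to be completed daily". The scores run from absent (0) to severe (3).

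**The concern.** Headache, aches, chills and fatigue are non-specific. They belong to influenza, but a tablet could also cause them. An investigator who believes the product is making one of them worse meets an instruction not to record it as a separate AE, and the text does not say that the instruction lapses once the product is suspected.

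What could be lost is the individual causality judgement, which has to be made at the time. A later analysis plan can tabulate diary scores by arm, but it cannot recover a judgement that was never written down. The Introduction describes the study as the first test of humic acid on flu symptoms in humans, so single suspected reactions are worth keeping.

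**Working it through.** No arithmetic applies. The check is to follow one event through the protocol and look for any sentence that lifts the exemption.

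**Illustrative event (assumed, not from the documents).** A subject's headache has settled and then returns after doses of study product. It is not serious. The investigator suspects the tablets.

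| Step | What the protocol provides | Result under a literal reading |
|---|---|---|
| Is it a flu symptom? | Headache is in inclusion criterion 4, Appendix 2 and Appendix 3 | Yes, so the 7.1.1 exemption can be applied |
| AE record | General rule for worsening conditions, then the flu exemption (7.1.1) | None required |
| Causality | Decided by the investigator for AEs (7.1.1) | Not triggered |
| Follow-up | For AEs, with emphasis on those suspected to be product-related (7.2.1) | Not triggered |
| Table by treatment | Counts AEs (8.2.3) | Not counted |
| Safety analysis | Haematology, chemistry and AEs (8.2) | Symptom scores are not listed |

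**Does another section restore the record?**

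- *Serious events (7.1.2).* The opening sentence is broad, but the list of outcomes applies to an event that is already an AE. It does not mention the flu exemption, and this event is not serious.
- *Unexpected reactions (7.1.3, 7.3).* Unexpectedness is judged against the product information, not against the usual course of influenza. A flu-like complaint consistent with that information would not qualify.
- *Withdrawal (4.4).* The circumstances are documented in detail, but only if the subject stops.
- *Adverse-effect diary entries and the visit question (6.1, 7.1.1, Appendix 1 footnote).* These may bring the complaint to light. They do not say whether a complaint that is also a flu symptom may then be entered as an AE.

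None of these sections states an exception.

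**Can the symptom score stand in for the AE record?** Only in part:

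- It holds severity and nothing on suspected cause or on what happened when the product was stopped. The causality categories in 7.1.1 depend on the latter.
- It cannot show worsening beyond severe.
- Sore throat is an illness symptom in inclusion criterion 4 and Appendix 2 but is not among the ten items of Appendix 3. For that symptom the stated reason for the exemption, that the daily scores capture it, does not hold.

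**The case against.** The strongest case on the other side has four parts.

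1. **Natural reading.** The exemption avoids double entry of the disease under study, whose symptoms are also the primary endpoint (Section 2). A headache caused by the tablets is not a flu symptom, so it was never exempt. A careful investigator may well read it this way. But the text leaves that reading to each investigator at two sites, and the literal instruction points the other way.
2. **Other routes exist.** Adverse effects have their own place in the diary, apart from the symptom scores. There is an open question at each visit, and serious events and unexpected reactions are reported. This stands, and it reduces the gap mainly to non-serious, flu-like worsening. It does not close it, as the working shows.
3. **Arm-level safety.** In a randomized, double-blind trial, a product that worsened these symptoms should show in the comparison of scores. That is partly right, but Section 8.2 averages scores over the available days, so the comparison gives mean severity by arm and no individual causality.
4. **The fix also rests on judgement.** True. However, it tells both sites that the judgement is to be recorded, which the present wording does not.

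A reader might infer three stronger points that the documents do not support:

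- *That humic acid is known to cause these symptoms.* No section says so.
- *That serious worsening of influenza would go unreported.* Sections 7.1.2 and 7.3 keep a general duty to report; the weakness is only that they do not refer to the exemption.
- *That the number of diary items shared with the illness definition measures the problem.* Nearly all items are shared (ear aches is the exception), but a count of scored items says nothing about how often a suspected reaction would go unrecorded.

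**Conclusion.** The point holds as a minor one. Section 7.1.1 fixes a collection rule that, followed as written, can remove a suspected non-serious reaction from the AE record, the causality assessment, AE follow-up and the AE table. Because it governs what is collected, it cannot be repaired at the analysis stage.

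No magnitude is claimed: the documents give no rate of product-related worsening and no basis for estimating how many records would be lost. The conclusion assumes that at least some investigators would apply the sentence literally. If all of them treated tablet-caused complaints as outside the exemption, nothing would be lost except explicit wording. The exemption itself is not at fault; only the absence of an exception is.

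**What to change.** Keep the exemption for the expected course of influenza and add to the sentence in Section 7.1.1:

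*except that a flu symptom is to be recorded as an adverse event, with causality, when it meets a seriousness criterion, when the investigator suspects a relationship to the investigational product, or when its severity or course is judged unexpected for influenza.*

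The seriousness limb links the exemption to Section 7.1.2. The suspected-relationship limb brings such events under 7.2.1 and 8.2.3. The clause would also cover sore throat, which has no daily score.

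The change is one clause. It needs no new visits, tests, forms or diary items. The downside is a few extra AE forms that rest on investigator judgement, some of which will describe ordinary influenza. Tables of diary worsening by arm can be left to the analysis plan.

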7.1.3 Unexpected Adverse Reaction

An unexpected adverse reaction is an adverse reaction, the nature and severity of which is not consistent with the applicable product information (e.g., Investigator's Brochure for an unapproved investigational product or package insert/summary of product characteristics for an approved product).

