7.3 Reporting of SAEs and Unexpected Adverse Reactions

Notification of any serious adverse events must be made in writing to the study sponsor within 24 hours of learning of the event. The IRB will be notified of all SAEs and unexpected adverse reactions.

A Pilot Study to Investigate the Effects of Humic Acid on Flu Symptoms

Protocol 10HFHL

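### The causality grades in 7.1.1 overlap and leave a gap: 'Not related' does not require the product to be ruled out, which affects relatedness labels and, with 'nature and severity' in 7.1.3, IRB notice of non-serious reactions

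*Protocol*

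**What the plan says.** Section 7.1.1 makes the investigator responsible for the grade: "The investigator will assess any AEs and decide causality". Five grades are defined.

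- 'Most probable', 'Probable' and 'Possible' all require a reasonable relationship to the product and differ only in dechallenge and rechallenge. For 'Possible' the text is: "There is a reasonable relationship between the investigational product and AE. Dechallenge information is lacking or unclear".
- 'Unlikely' requires a temporal relationship, but "there is no reasonable causal relationship between the investigational product and the AE".
- 'Not related' has two limbs joined by 'or': "No temporal relationship to the investigational product administration" is the first, and the second reads "or there is a reasonable causal relationship between non-investigational product, concurrent disease or circumstance and the AE".

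Section 7.1.3 defines an unexpected adverse reaction as one "the nature and severity of which is not consistent with the applicable product information". Section 7.3 requires written notice of any SAE to the sponsor within 24 hours, and adds: "The IRB will be notified of all SAEs and unexpected adverse reactions". Section 8.2.3 tabulates adverse events by body system and treatment, and reports causality for each.

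**The concern.** A causality scale works only if an event falls into one grade. Here the grade at the unrelated end can be reached through another plausible cause, without any judgement on the product. In this trial such a cause is built in: section 4 enrols adults with influenza A or B, and section 4.3 allows antipyretics, decongestants, expectorants and lozenges. Two sites could grade the same event at opposite ends and both be following the protocol.

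At stake is the meaning of the relatedness column in the report of a study that the Introduction calls the first test of humic acid's effects on flu symptoms in humans. The grade also matters for one reporting route. An unexpected adverse *reaction* presupposes that the event is attributed to the product, so a 'Not related' grade would keep a non-serious event off that route.

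**Working it through.** No arithmetic applies. The check reads each grade as a set of conditions, runs test events through them, and then traces where the grade is used.

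**Conditions in 7.1.1**

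| Grade | Link to product | Other cause | Dechallenge |
|---|---|---|---|
| Most probable | reasonable | not addressed | responds, and recurs on rechallenge where feasible |
| Probable | reasonable | not addressed | responds |
| Possible | reasonable | not addressed | lacking or unclear |
| Unlikely | temporal only, no reasonable causal link | not addressed | not addressed |
| Not related, limb 1 | no temporal link | not addressed | not addressed |
| Not related, limb 2 | not addressed | reasonable | not addressed |

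None of the three related grades asks that other causes be absent, and limb 2 does not ask that the product be absent.

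**Test events**

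1. Reasonable product link, reasonable other cause, dechallenge unknown: meets 'Possible' and 'Not related'.
2. As 1, but the event resolves on withdrawal: meets 'Probable' and 'Not related'. With recurrence on rechallenge: 'Most probable' and 'Not related'.
3. Reasonable product link, no other cause, no response to withdrawal: meets nothing. 'Probable' needs a response, 'Possible' needs "Dechallenge information is lacking or unclear", and 'Unlikely' needs the absence of a reasonable link. If another cause is present, 'Not related' is the only grade that fits.
4. Temporal link only, other cause present: meets 'Unlikely' and 'Not related'. These grades are adjacent and both deny a product link, so little turns on it.

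A concrete instance of event 1 is a raised ALT in a subject taking an antipyretic. Section 7.1.4 cites AST and/or ALT above 2 x ULN. After baseline, Appendix 1 schedules chemistry only at Day 14, the end of treatment, so dechallenge information may be lacking when the event is graded. If the investigator finds both links reasonable, both grades fit.

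**Expectedness in 7.1.3**

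| Nature inconsistent | Severity inconsistent | 'and' | 'or' |
|---|---|---|---|
| yes | yes | unexpected | unexpected |
| yes | no | not unexpected | unexpected |
| no | yes | not unexpected | unexpected |
| no | no | not unexpected | not unexpected |

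The case that matters in practice is the third: a known type of reaction at greater than described severity.

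**Where the grade or expectedness is used**

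| Route | Depends on it? |
|---|---|
| Recording of adverse events (7.1.1) | no |
| SAE to sponsor and to IRB (7.3) | no |
| Adverse event table by treatment, all randomized subjects (8.2, 8.2.3) | no |
| Causality reported per event (8.2.3) | yes |
| IRB notice of non-serious unexpected reactions (7.1.3, 7.3) | yes |
| Follow-up (7.2.1) | emphasis only; adverse events in general are followed |
| Withdrawal (4.4) | named in one example of an open list |

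**The case against.** The strongest reply is that the main safety routes ignore causality. This stands. A reader might infer that product reactions disappear from reporting. They do not: every SAE reaches the sponsor and the IRB whatever its grade, and every adverse event is recorded and counted by arm.

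Three further limits also stand. First, 7.1.1 captures worsening flu symptoms as symptom scores and not as adverse events, so typical influenza complaints never reach the scale. Second, a reader might infer that the error runs only toward too few related events, or that it differs between arms. Neither is shown: the text permits either grade, an event due to influenza can equally be called 'Possible', and the trial is double-blind with influenza in both arms. Third, the list in 4.4 is open and rests on the Principal Investigator's judgement, so a 'Not related' grade blocks nothing there.

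On 7.1.3, the phrase can be read as nature and severity taken together, and its effect depends on product information that is not shown. Section 10 names only venipuncture as a risk. If no reaction is listed, any reaction would be inconsistent on both counts and the 'and' would exclude nothing.

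A reader might also infer that the sponsor alone would see non-serious unexpected reactions from both sites, so that its lack of notice is a gap. Section 7.3 speaks of one IRB, and nothing says that the two sites use different ones.

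It can be argued that a negative dechallenge counts against causation and belongs under 'Unlikely'. That is a defensible policy, but it is not what the definition of 'Unlikely' says.

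None of this removes the overlap, the missing tie-break or the unplaced case.

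**Conclusion.** The causality scale is badly fixed as written. 'Not related' overlaps with all three related grades, and an event reasonably linked to the product that did not respond to withdrawal has no grade unless another cause admits it to 'Not related'. Influenza is present in all 40 planned subjects, so the overlap is open for any adverse event, other than a flu symptom, that influenza or a symptom medicine could reasonably explain.

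The consequence is confined to two things: the causality label reported for each event, and IRB notice of non-serious unexpected reactions. The second is further narrowed if 'nature and severity' is read literally and the product information lists reactions. The documents give no rate of such events, so no figure can be put on the misgrading. The by-arm comparison of adverse events and the reporting of serious events are sound on this point.

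**What to change.** 1. In 7.1.1, redefine 'Not related' as: no temporal relationship; or another cause explains the event **and** there is no reasonable relationship to the investigational product. Test events 1 and 2 then fall only in the related grades.
2. Assign the case of a reasonable product link with no response to dechallenge to a named grade. 'Possible' is the natural place, since it already holds reasonable links without a positive dechallenge.
3. In 7.1.3, replace 'nature and severity' with 'nature or severity'.

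After the first change, 'Unlikely' and 'Not related' still touch when another cause is present (test event 4). If strict separation is wanted, confine 'Unlikely' to events with no other identified cause.

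The cost is a few sentences in two subsections. In use, a few more events will be graded 'Possible' and a few more notices will go to the IRB. No data collection, visit or analysis changes.
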